5.6.2. Risks

The known and potential risks of OCA and BZF are described in the FDC Investigator's Brochure and are summarized in Table 1 and Table 2, respectively.

Table 1: Known and Potential Risks of OCA

OCA
Hepatic Adverse Events
Hepatic failure, sometimes fatal or resulting in liver transplant, has been reported with OCA treatment in PBC patients with decompensated cirrhosis.
Some of these cases occurred in patients with decompensated cirrhosis when they were treated with higher than the recommended dosage for that patient population; however, cases of hepatic decompensation and failure have continued to be reported in patients with decompensated cirrhosis even when they received the recommended dosage. Per the CCDS v5.0, Ocaliva is contraindicated in patients with PBC with decompensated cirrhosis (e.g., Child-Pugh Class B or C) or a prior decompensation event and in patients with complete biliary obstruction. Ocaliva is also contraindicated in patients with compensated cirrhosis with evidence of portal hypertension (e.g. ascites, gastroesophageal varices, persistent thrombocytopenia).
A dose-response relationship was observed for the occurrence of hepatic adverse reactions including jaundice, worsening ascites and primary biliary cholangitis flares with dosages of OCA of 10 mg once daily to 50 mg once daily (up to 5-times the highest recommended dosage), as early as one month after starting treatment with OCA in two 3-month placebo-controlled clinical trials in patients with primarily early stage PBC.

In a pooled analysis of three placebo-controlled clinical trials, in patients with primarily early stage PBC disease, the exposure-adjusted incidence rates for all serious and otherwise clinically significant hepatic adverse reactions, and isolated elevations in liver biochemical tests, per 100 PEY were: 5.2 in the OCA 10 mg group (highest recommended dosage), 19.8 in the OCA 25 mg group (2.5-times the highest recommended dosage) and 54.5 in the OCA 50 mg group (5-times the highest recommended dosage) compared to 2.4 in the placebo group.

Pruritus

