^a Interrupt study drug; Initiate workup of competing etiologies and close monitoring (repeat labs and exam 2-3 times per week), including repeat labs initially.

- Study drug can be restarted after a minimum of 30 days if another etiology is identified, liver enzymes return to baseline, lab abnormalities are determined not to be due to DILI, no symptoms, and approved by the Medical Monitor and Investigator.
- If study drug is restarted after 30 days, repeat labs in 2-5 days for ALT, AST, and TB or 7-10 days for ALP as indicated and continue close monitoring.

^b New baseline values for DILI monitoring for ALT, AST, ALP, TB should be determined based upon average of Month 3 and Month 6 values if average is $>50\%$ decrease from original baseline. Adapted from [Palmer 2020](#).

^c Liver signs and symptoms to include: new onset severe fatigue or significant worsening of baseline fatigue; new onset severe pruritus or significant worsening on baseline pruritus; nausea, vomiting, right upper quadrant pain; fever, rash, or $>5\%$ eosinophilia; new onset of hepatic decompensation (e.g., ascites, variceal bleeding, hepatic encephalopathy).

^d Symptoms of rhabdomyolysis may include muscle swelling; weak, tender or sore muscles; dark urine; fever; tachycardia; nausea and vomiting; confusion; dehydration; or abdominal pain.

^e If IP interrupted due to CK trigger, closely monitor CK and creatinine/renal function in addition to liver biochemistries every 2 weeks until values return to baseline levels; same criteria apply to considering re-initiation of IP. CK levels should be assessed in patients reporting symptoms of rhabdomyolysis, and investigational product should be discontinued if markedly elevated CK levels (≥ 5 x ULN) occur or myopathy is diagnosed.

It should be noted that it is difficult to recognize every potential marker of hepatic deterioration or muscular injury. There is no substitute for good medical judgment. Investigators will be reminded to be cautious and mindful in their evaluation of subjects' symptoms, signs, and laboratory results. However, for example, a single abnormal laboratory analyte result may be artifactual; accordingly, Investigators will be allowed to implement an alternate follow-up procedure if considered appropriate based on their medical judgement but only after documented agreement with the Sponsor's Medical Monitor.

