7.4.3. Clinical Criteria for Monitoring for Potential Hepatic Decompensation Events

Subjects will be monitored for potential hepatic decompensation events throughout the study. Investigational product is to be permanently discontinued with the development of any clinical events listed in Table 5.

Subjects who experience hepatic decompensation events should be closely monitored until normalization or stabilization using good clinical judgement, and, per Food and Drug Administration (FDA) guidance for observation of potential DILI, should include, but not be limited to, a thorough clinical evaluation including repeat liver enzymes and tests of liver function two to three times weekly with subsequent frequency to be determined by clinical status; complete history and physical; evaluation of concomitant drugs, alcohol, illicit drug use; concomitant liver conditions including viral hepatitis; environmental exposures; consider gastroenterology or hepatology consultation.

After stabilization, subjects should continue with scheduled study visits for safety follow up.

Table 5: Clinical Criteria for Monitoring Potential Hepatic Decompensation Events and Mandatory Discontinuation of Investigational Product

 • Clinical evidence of portal hypertension, defined as 
 ○ Platelet count <150,000/μL ○ Splenomegaly on ultrasound ○ Non-bleeding varices on endoscopy • Evidence of hepatic decompensation 
 ○ Progression to CP score ≥7 ○ Ascites including hepatic hydrothorax ○ Hepatic encephalopathy – requiring hospitalization and/or lactulose and/or rifaximin ○ Hepatorenal syndrome (Type 1 or Type 2), hepatopulmonary syndrome, or portopulmonary syndrome ○ Variceal hemorrhage ○ Jaundice (with total bilirubin >3 mg/dL [$>51.3 \mu\text{mol/L}$]) ○ MELD ≥15 • HCC • Any liver-related event requiring hospitalization and treatment • Evaluation, listing, or completion of a liver transplant
--

CP=Child-Pugh; HCC=hepatocellular carcinoma; MELD=Model for End-stage Liver Disease

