7.4.4.1. Criteria for Assessing Cirrhosis

Acceptable methods of confirming (via medical history) or assessing cirrhosis include documented evidence or presence of one or more of the following cirrhosis indicators:

- Biopsy results consistent with PBC Stage 4 (Ludwig 1978)
- TE Median Value ≥ 16.9 kPa (Corpechot 2012)
- The presence of any of the following in the absence of acute liver failure:
 - Varices
 - Ascites
 - Radiological evidence of cirrhosis (e.g., nodular liver or enlargement of portal vein and splenomegaly)
- Combined low platelet count ($<150,000/\mu\text{L}$) with:
 - Persistent decrease in serum albumin, or
 - Elevation in PT/INR (not due to antithrombotic agent use), or
 - Elevated bilirubin (2x ULN)

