 5. Presence of any other disease or condition that interferes with the absorption, distribution, metabolism, or excretion of drugs including bile salt metabolism in the intestine (e.g., inflammatory bowel disease or gastric bypass procedure [gastric lap band is acceptable])
 6. Evidence or history of cholelithiasis or choledocholithiasis unless documented cholecystectomy. Gallbladder polyps if >5 mm in diameter
 7. History of chronic pancreatitis or recurrent acute pancreatitis – defined as at least 2 episodes of acute pancreatitis, with symptoms resolving between each episode
 8. History of drug-induced myopathy
 9. Chronic kidney disease (serum creatinine >1.5 mg/dL [>135 µmol/L]; CrCl <60 mL/min) or undergoing dialysis
 10. Platelet count <150,000/µL at the last visit in parent study, before transitioning to Study 977-311
 11. Known history of human immunodeficiency virus (HIV) infection
 12. History or presence of clinically concerning cardiac arrhythmias likely to affect survival during the study, QT interval of the electrocardiogram (QT) or QT interval of the electrocardiogram corrected (QTc) interval of >450 milliseconds for males and >470 milliseconds for females
 13. Severe pruritus, or required systemic treatment for pruritus (e.g., with bile acid sequestrants [BAS] or rifampicin) within 2 months of Day 1 of Study 977-311. Subjects who plan to use or will use BAS during the study will not be eligible.
 14. History of known or suspected clinically significant (CS) hypersensitivity to OCA, BZF, or other fibrates or any of their components

15. Known photoallergic or phototoxic reactions to fibrates
16. If female, known pregnancy, a positive urine pregnancy test (confirmed by a positive quantitative serum pregnancy test), or current lactation at the last visit in parent study, before transitioning to Study 977-311
17. Other CS medical conditions that are not well controlled or for which medication needs are anticipated to change during the study (e.g., Type 2 diabetes mellitus, hypothyroidism, nephritic or nephrotic syndrome, dysproteinemia, obstructive biliary disease, dyslipidemia), and/or up to the discretion of the Principal Investigator

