8.4.1. Reasons for Mandatory Discontinuation of Investigational Product

Subjects will be monitored for potential hepatic decompensation events throughout the study. Clinical criteria for monitoring these events are summarized in [Table 5](#).

Investigational product will be discontinued permanently if the subject has evaluation, listing or completion, of a liver transplant or experiences other potential hepatic decompensation events as defined in Table 5. Subjects should be closely monitored until normalization or stabilization and should continue to return for scheduled study visits for safety follow-up.

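### Table 5 makes a platelet count below 150,000/µL, the same figure as the entry limit, a permanent-stop criterion without saying whether one value is enough, and other sections treat low platelets differently

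*Protocol*

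**What the plan says.** Entry: Protocol section 8.3, criterion 10, excludes subjects with "Platelet count <150,000"/µL at the last parent-study visit.

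On study: Table 5 (section 7.4.3) opens with "Clinical evidence of portal hypertension, defined as" and then lists three items: the same platelet figure, splenomegaly on ultrasound, and non-bleeding varices on endoscopy. No word joins the three. No repeat sample, persistence or fall from baseline is mentioned.

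Consequence: section 7.4.3 says "Investigational product is to be permanently discontinued with the development of any clinical events listed in Table 5". Section 8.4.1 repeats the permanent stop for a subject who "experiences other potential hepatic decompensation events as defined in Table 5", without exception. In both sections the subject stays in follow-up.

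Elsewhere:
- Table 1 (section 5.6.2) describes the contraindication as "evidence of portal hypertension (e.g. ascites, gastroesophageal varices, persistent thrombocytopenia".
- Section 7.4.2, after Table 4, warns that "a single abnormal laboratory analyte result may be artifactual" and lets the Investigator follow up differently after documented agreement with the Sponsor's Medical Monitor. Neither 7.4.3 nor 8.4.1 refers to this.
- Section 7.4.2 also says that the laboratory thresholds triggering interruption are in Table 5, whereas Table 5 is titled as mandatory discontinuation.

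SAP section 10.2.1 does not count an AE starting more than 30 days after the last dose as treatment-emergent. Section 10.2.3 restricts all AE summaries to treatment-emergent events.

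**The concern.** A subject may enter at or just above 150,000/µL, and the same figure then applies as a stop criterion at each later visit. Read literally, one count of 149,000 in a subject whose true level has not moved ends treatment for good. Read with Table 1, or with the single-result provision in 7.4.2, the same count need not do so. Sites could reasonably act differently on identical results.

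At stake is time on drug in a study whose primary objective is long-term safety and tolerability. Follow-up visits continue after a stop, but new adverse events more than 30 days after the last dose appear only in listings, not in the summary tables. A stop caused by measurement and biological variation therefore also shortens the summarised safety record of a subject who was correctly enrolled.

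**Working it through.** The plan gives no crossing rate, so there is no figure to reproduce.

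**Visits (Protocol section 7.1.1, Table 3).** Hematology, which includes platelets (Table 11), is drawn at Months 1, 3, 6, 12, 18, 24, 30, 36, 42, 48, 54 and 60: 12 post-baseline visits. No product is dispensed at Month 60, so a low count can still stop treatment at 12 − 1 = 11 of them.

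**Assumptions, not in the documents.** Within-subject CV of 5%, 7% or 9%; a stable true count; log-normal variation independent between visits; all 11 visits attended on drug; one low value sufficient.

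**Formulas.** Per visit, p = Φ(ln(150/true)/CV), with counts in thousands. Over 11 visits, P = 1 − (1 − p)^11.

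**Worked case.** True count 160, CV 5%: ln(150/160) = −0.0645; divided by 0.05 this is −1.29; p = 0.098; P = 1 − 0.902^11 = 0.68.

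| True count (/µL) | p per visit, CV 5/7/9% | At least one value <150,000 in 11 visits |
|---|---|---|
| 155,000 | 0.256 / 0.320 / 0.358 | 96 / 99 / 99% |
| 160,000 | 0.098 / 0.178 / 0.237 | 68 / 88 / 95% |
| 170,000 | 0.006 / 0.037 / 0.082 | 7 / 34 / 61% |

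**Sensitivity to independence.** With correlation 0.5 between adjacent visits (normal variation, 12 visits, CV 5% / 10%), the chances are 90 / 97% at 155,000, 61 / 90% at 160,000 and 9 / 66% at 170,000. Correlation lowers the figures but does not change the pattern.

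**Cohort size.** The baseline platelet distribution is not given. Assume true counts are normal with mean 220-260 and SD 50-60 (thousand/µL), and that the entry and Day 1 counts are both at least 150. Simulation over the three CVs and 11 visits gives 0.9% to 8.3% of subjects with at least one low value: 0.009 × 133 ≈ 1 to 0.083 × 133 ≈ 11. About 4-8% of those subjects have a true count below 150,000, so not every crossing is noise.

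**The case against.** **The 7.4.2 provision may already cover this.** That section's title includes potential hepatic decompensation, it points to Table 5 for laboratory thresholds, and a platelet count is a laboratory analyte. On that reading a single low value can be handled otherwise with the Medical Monitor's agreement. This stands as a possible reading. It does not settle the matter: the provision is optional, the analytes listed under Figure 2 do not include platelets, the Table 5 reference may be a slip for Table 4, and the two sections ordering the stop do not mention it.

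**Platelets alone may not suffice.** If the three portal-hypertension items were all required, noise in one of them would not trigger a stop. The reference to any listed event favours the single-item reading but is not decisive. This too stands, as part of the ambiguity.

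**The cirrhosis criteria are no contradiction.** Section 7.4.4.1 uses "Combined low platelet count" with another finding, but it defines cirrhosis, not portal hypertension. The objection is right, and the point does not rely on that section.

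**A stop limit equal to the entry limit is a legitimate cautious choice.** Agreed. The point is that the plan does not apply one reading consistently.

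**A reader might infer that false crossings inflate the hepatic safety signal.** The documents do not support this. Suspected liver outcomes go to independent adjudication (Protocol section 14.3), the SAP defines hepatic injury by a MedDRA query, and no visible passage or SAP table records a low count as a portal hypertension event.

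**Conclusion.** The inconsistency stands on the text alone. The sections do not agree on whether one platelet value below 150,000/µL requires permanent discontinuation, and Table 5 does not say how its three items combine.

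If one value suffices, a stable subject within about 5,000 of the limit is very likely to be stopped by noise. At a true 160,000 the chance is 68-95%, and at 170,000 it is 7-61%. These figures rest on the assumed CV, independent visits and full attendance. It would be too strong to say that subjects just above the limit will cross it: beyond the immediate neighbourhood of 150,000 the answer depends heavily on the CV, and the number of subjects that close is not in the documents. The estimate of 1-8% (roughly 1-11 of 133) holds only under the assumed baseline distribution.

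The supported consequence is lost drug exposure and, through the SAP's 30-day rule, later adverse events missing from the summaries.

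**What to change.** **Protocol.** Reconcile Table 1, section 7.4.2 (both the single-result provision and the interruption reference to Table 5), section 7.4.3 with Table 5, and section 8.4.1 on three questions:
1. Is one platelet value alone a Table 5 event?
2. Are the three portal-hypertension items alternatives, or are they required together?
3. Does the single-result provision in 7.4.2 apply to Table 5?

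The clinical rule is the sponsor's to choose.

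**SAP.** Report discontinuations triggered by platelet count alone as a separate category, showing for each subject any later platelet count, scheduled or unscheduled. This displays the events without redefining them.

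**Cost.** A clarification at the next amendment and one extra table; no added visits. The triggering Table 5 item must be identifiable in the data, which the documents do not confirm. Later counts may be six months away after Month 12 and will be off drug, so they will not always show whether the first value was noise.

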7.4.4. Child-Pugh Score

CP Score (Pugh 1973, Lucey 1997) is calculated and reported within the electronic data capture (EDC) system based on data entered into the eCRF by adding the scores from the 5 factors outlined in Table 6 and can range from 5 to 15. The Investigator should ensure all lab data is entered into the eCRF. Although CP score calculation will automatically be computed in all subjects (at all times data is obtained for the eCRF), it should only be applied to subjects who meet the criteria for progression to cirrhosis (see Section 7.4.4.1). Dose adjustment or discontinuation should not be considered based solely on the CP score in subjects who do not meet criteria for presence of cirrhosis.

A total score of 5 to 6 is considered Class A; a score of 7 to 9 is Class B (moderate, significant functional compromise); and a score of 10 and above is Class C (severe, decompensated

disease). The calculation of the CP Score includes Investigator assessments of ascites and hepatic encephalopathy, which may be assessed during the AE review at the scheduled visits, as well as total bilirubin, serum albumin, and prothrombin time (PT), the data for which will be obtained from the central laboratory.

Table 6: Child-Pugh Scoring System

Factor	Units	Points		
		1	2	3
Serum bilirubin	μmol/L	<34	34-50	>50
	mg/dL	<2.0	2.0-3.0	>3.0
Serum albumin	g/L	>35	28-35	<28
	g/dL	>3.5	2.8-3.5	<2.8
Prothrombin time	Seconds prolonged	0-3	4-6	>6
	INR	<1.7	1.7-2.3	>2.3
Ascites		None	Mild	Moderate-Severe
Hepatic encephalopathy ^a		No	Grade 1 or 2	Grade 3 or 4

CP=Child-Pugh; INR=international normalized ratio

The CP score is calculated by adding the scores for the 5 factors and can range from 5-15. CP class is either A (a score of 5-6), B (7-9), or C (10 or above). Decompensation indicates cirrhosis with a CP score of 7 or more (Class B).

^a Grade 0: normal consciousness, personality, neurological examination, electroencephalogram.

Grade 1: restless, sleep disturbed, irritable/agitated, tremor, impaired handwriting, 5 cps waves.

Grade 2: lethargic, time-disoriented, inappropriate, asterixis, ataxia, slow triphasic waves.

Grade 3: somnolent, stuporous, place-disoriented, hyperactive reflexes, rigidity, slower waves.

Grade 4: unrousable coma, no personality/behavior, decerebrate, slow 2-3 cps delta activity.

Child-Pugh criteria: (Pugh 1973, Lucey 1997, Vilstrup 2014).

7.4.4.1. Criteria for Assessing Cirrhosis

Acceptable methods of confirming (via medical history) or assessing cirrhosis include documented evidence or presence of one or more of the following cirrhosis indicators:

- Biopsy results consistent with PBC Stage 4 (Ludwig 1978)
- TE Median Value ≥ 16.9 kPa (Corpechot 2012)
- The presence of any of the following in the absence of acute liver failure:
 - Varices
 - Ascites
 - Radiological evidence of cirrhosis (e.g., nodular liver or enlargement of portal vein and splenomegaly)
- Combined low platelet count ($<150,000/\mu\text{L}$) with:
 - Persistent decrease in serum albumin, or
 - Elevation in PT/INR (not due to antithrombotic agent use), or
 - Elevated bilirubin (2x ULN)

7.4.4.2. Mayo Risk Score

Mayo Risk Score (MRS) ([Dickson 1989](#)) is reported within the EDC system based on data entered into the eCRF. Calculation of MRS includes Investigator assessment of peripheral edema and the use of diuretic therapy, which will be assessed during AE and concomitant medicine review at the scheduled visits and entered into the eCRF, as well as total bilirubin, albumin, and PT results obtained from the central laboratory data.

7.4.4.3. Potential Myopathy Evaluation and Monitoring

Subjects will be monitored for potential myopathy events throughout the study. If a subject becomes aware of the development of signs and symptoms of potential myopathy (i.e., muscle weakness, muscle soreness or muscle pain), the subject will be instructed to promptly contact the site for further assessment.

Clinical criteria for the monitoring of these events and the interruption/discontinuation of investigational product is as follows:

- At Day 1/Day 2: Check baseline CK: If ≥ 5 x ULN the Medical Monitor and Sponsor Medical Monitor will determine if the subject can continue in Study 977-311 on a case-by-case basis.
- Previous History of Myalgia: Yes or No. If Yes, rate on a scale of 1 to 10 with 1 being the least amount of discomfort and 10 being the most amount of discomfort to establish baseline.
- If subjects develop symptoms of myopathy at any point during the study, CK values must be checked. A CK ≥ 5 x ULN or ≥ 3 x ULN with symptoms consistent with rhabdomyolysis will require investigational product interruption. Laboratory values including CK and creatinine will be closely monitored until values return to baseline levels (see [Table 4](#)).

7.5. Medical Management of Subjects with Symptomatic Cholelithiasis and/or Cholecystitis

If a subject experiences symptoms suggestive of cholelithiasis and/or cholecystitis, the subject should undergo a complete evaluation consistent with the local standard of care, be assessed for appropriate treatment, including potential indication for surgery (e.g., cholecystectomy), and be monitored until resolution of clinical signs and symptoms. If symptomatic cholelithiasis and/or cholecystitis is diagnosed, particularly with any suspicion of biliary obstruction, investigational product should be promptly interrupted. Treatment with investigational product may be resumed if an alternative probable cause has been found and resolution has occurred.

Investigational product should be discontinued in the following instances:

1. Development of choledocholithiasis
2. Development of acute cholecystitis
3. Presence of any gallbladder polyp >5 mm

7.6. Dosage Adjustment Criteria

Dose frequency may be modified for the management of pruritus as described in [Section 14.1.3.1](#). In the event of tolerability issues such as pruritus, the dosing frequency may be decreased at the discretion of the Investigator.

Subjects can be discontinued from investigational product by the Investigator at any time for clinical safety concerns. Subjects who are discontinued from investigational product should be requested to continue with study visits until Month 60/end of study (EOS). Subjects who discontinue investigational product may be requested to come in for an Unscheduled Visit at the discretion of the Investigator depending on the timing of their next scheduled study visit.

Refer to [Section 8.4.1](#) for guidance on mandatory discontinuation of investigational product due to severe and related AEs. Refer to [Section 8.4.2](#) for other reasons of discontinuation of investigational product (e.g., withdrawal of consent, lost to follow-up, or pregnancy).

Subjects who were taking UDCA should continue this as a concomitant medication for the entirety of the study unless there is a tolerance or safety event related to UDCA that would require discontinuation.

